4.2 Enrollment Guidelines

Eligible patients will be identified by the principal investigator and co-investigators of this study. Potentially eligible patients will be screened in the University of Kentucky Markey Cancer Center clinics by the investigators, study personnel, and the Principal Investigator (PI). Upon obtaining proper consent, patients will be enrolled into the study.

4.3 Informed Consent

The goal of the informed consent *process* is to provide people with sufficient information so they can make informed choices about whether to begin or continue participation in clinical research. The process involves a dynamic and continuing exchange of information between the research team and the participant throughout the research experience. It includes discussion of the study's purpose, research procedures, risks and potential benefits, and the voluntary nature of participation.

The informed consent *document* provides a summary of the clinical study and the individual's rights as a research participant. The document acts as a starting point for the necessary exchange of information between the investigator and potential research participant. Also, research participants and their families may use the consent document as an information resource and reference throughout participation in the trial. The informed consent *document* is often considered the foundation of the informed consent process; it does not, however, represent the entirety of the process. Nor is the informed consent document a risk-management tool for the investigator and/or institution.

The investigator must explain to each subject (or legally authorized representative) the nature of the study, its purpose, the procedures involved, the expected duration, the potential risks and benefits involved and any discomfort it may entail. Each subject must be informed that participation in the study is voluntary and that he/she may withdraw from the study at any time and that withdrawal of consent will not affect his/her subsequent medical treatment or relationship with the treating physician.

This informed consent should be given by means of a standard written statement, written in non-technical language. The subject should read and consider the statement before signing and dating it, and should be given a copy of the signed document. If the subject cannot read or sign the documents, oral presentation may be made or signature given by the subject's legally appointed representative, if witnessed by a person not involved in the study, mentioning that the patient could not read or sign the documents. No patient can enter the study before his/her informed consent has been obtained. The informed consent form is considered to be part of the protocol, and must be submitted by the investigator with the protocol at the time of IRB review.

4.4 Compliance with Laws and Regulations

The study will be conducted in accordance with U.S. Food and Drug Administration (FDA) and International Conference on Harmonization (ICH) Guidelines for Good Clinical Practice (GCP), the Declaration of Helsinki, any applicable local health authority, and Institutional Review Board (IRB) requirements. The PI or designee will be responsible for obtaining continuing and not less than annual IRB re-approval throughout the duration of the study. Copies of the Investigator's annual report to the IRB and copies of the IRB continuance of approval must be maintained by the MCC CRDM SRF. The PI or designee is also responsible for notifying the Data and Safety Monitoring Committee of the MCCC and the UK IRB of any significant adverse events that are serious and/or unexpected, as per SOP's of those entities. The MCC DSMC will review all

adverse events of this IIT as per its SOP.

5. TREATMENT PLAN

5.1 Enrollment and Screening Process

Prior to any study-required tests, subjects must first provide written informed consent to participate in this study. All lab tests and radiographic studies should be completed within 4 weeks prior to initiation of treatment. Complete history, physical examination, and evaluation of Performance Status. Required lab work will include: complete blood count (CBC) with differential; serum chemistry tests to include alkaline phosphatase, glucose, creatinine, electrolytes, AST (SGOT), and total bilirubin.

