3. PATIENT SELECTION

3.1 Eligibility Criteria

- 3.1.1 Patients must have a histologically confirmed or highly suspected (as determined by treating physician) solid tumor that is planned for surgical resection.
- 3.1.2 Age ≥ 18 years.
- 3.1.3 ECOG performance status ≤ 2 (Karnofsky $\geq 60\%$, see Appendix A).
- 3.1.4 Patients must be able to ingest oral medications (crushing and administering via PEG tube is acceptable).
- 3.1.5 Patients must have normal organ and marrow function as defined below:
- absolute neutrophil count $\geq 1,500/\text{mcL}$
 - platelets $\geq 100,000/\text{mcL}$
 - total bilirubin Less than 1.5 x ULN
 - AST(SGOT)/ALT(SGPT) $\leq 2.5 \times$ institutional upper limit of normal
 - creatinine less than institutional ULN
- OR
- Creatinine clearance $\geq 60 \text{ mL/min/1.73 m}^2$ for patients with creatinine levels above institutional normal.
- 3.1.6 Patients must be able to undergo surgical resection of their tumor as determined by the treating surgeon.
- 3.1.7 The effects of hydroxychloroquine on the developing human fetus are unknown. For this reason and because anti-malarial agents as well as other therapeutic agents used in this trial are known to be teratogenic, women of child-bearing potential and men must agree to use adequate contraception (hormonal or barrier method of birth control; abstinence) prior to study entry and for the duration of study participation. Should a woman become pregnant or suspect she is pregnant while she or her partner is participating in this study, she should inform her treating physician immediately. Men treated or enrolled on this protocol must also agree to use adequate contraception prior to the study, for the duration of study participation, and 4 months after completion of hydroxychloroquine administration.
- 3.1.8 Ability to understand and the willingness to sign a written informed consent document.

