- 3.2.8 Pregnant women are excluded from this study. While hydroxychloroquine has not been formally assigned to a pregnancy category by the FDA, animal studies have revealed that the drug passed rapidly across the placenta, accumulated selectively in the melanin structures of the fetal eyes, and was retained in the ocular tissues for five months after the drug had been eliminated from the rest of the body. There are no controlled data in human pregnancy. Because there is an unknown but potential risk for adverse events in nursing infants secondary to treatment of the mother with hydroxychloroquine, breastfeeding should be discontinued if the mother is treated with hydroxychloroquine. These potential risks may also apply to other agents used in this study.
- 3.2.9 HIV-positive patients on combination antiretroviral therapy are ineligible because of the potential for pharmacokinetic interactions with hydroxychloroquine. In addition, these patients are at increased risk of lethal infections when treated with marrow-suppressive therapy. Appropriate studies will be undertaken in patients receiving combination antiretroviral therapy when indicated.

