5.6 Duration of Therapy

In the absence of treatment delays due to adverse event(s), treatment will continue for 14 days or until one of the following criteria applies:

- Disease progression,
- Intercurrent illness that prevents further administration of treatment,
- Unacceptable adverse event(s),
- Patient decides to withdraw from the study, or
- General or specific changes in the patient's condition render the patient unacceptable for further treatment in the judgment of the investigator.

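### The single scheduled pregnancy test has no window of its own and may be 28 days old at the first hydroxychloroquine dose

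*Combined protocol and SAP*

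**What the plan says.** Section 3.2.8 is unconditional: "Pregnant women are excluded from this study". It names neither a type of test nor a time for it.

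The Study Calendar has one pregnancy-test row, for females of child-bearing potential. It is marked at Pre-Study and blank in every later column, with no footnote. The lab list in section 5.1 (blood count and serum chemistry) does not mention the test. Its timing therefore rests on two general rules:

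- Section 5.1: "All lab tests and radiographic studies should be completed within 4 weeks prior to initiation of treatment".
- The sentence above the calendar, which places baseline evaluations 2-4 weeks before the start of protocol therapy.

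The calendar's one provision for repeating laboratory work concerns a patient whose condition is deteriorating.

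On the hazard, section 3.1.7 states "The effects of hydroxychloroquine on the developing human fetus are unknown" and adds that "anti-malarial agents as well as other therapeutic agents used in this trial are known to be teratogenic". The same section has women of child-bearing potential agree to contraception "prior to study entry and for the duration of study participation". If a woman becomes pregnant or suspects it, "she should inform her treating physician immediately".

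**The concern.** An exclusion protects a patient only if it is verified close enough to exposure. A negative test says nothing about a conception that came after it. A site that follows this plan exactly may screen a woman, wait four weeks, and give the first dose with no further check of pregnancy status.

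Read literally, the calendar's 2-4 weeks makes this worse. A test done in the last 14 days before dosing, which is the more informative one, would fall outside the baseline window.

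What is at stake is fetal exposure to one course of HCQ: 14 days, extendable by 7 (section 5.2). It would require a pregnancy that began after the screening test, after contraception failed, and that the woman did not suspect. The protocol's own language on fetal risk, including the animal data on placental transfer and ocular retention in 3.2.8, supports precaution. It does not establish human harm.

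**Working it through.** No sample size, power or error rate is involved. The check compares the relevant sections and converts weeks to days.

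**Inputs**

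- General laboratory window: up to 4 weeks before treatment (5.1).
- Baseline window: 2-4 weeks before therapy (Study Calendar).
- Scheduled pregnancy tests: one, at Pre-Study (Study Calendar).
- Dosing: 14 days, extendable by 7 (5.2).
- Planned women: 9 of 18 (accrual table, 3.3). The number of child-bearing potential is not given.

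**Permitted age of the test at first dose**

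| Rule | Minimum | Maximum |
|---|---|---|
| Section 5.1 | 0 days | 4 × 7 = 28 days |
| Calendar, read literally | 2 × 7 = 14 days | 4 × 7 = 28 days |
| Calendar, read as up to 4 weeks | 0 days | 4 × 7 = 28 days |
| Proposed 7-day window | 0 days | 7 days |

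The maximum is 28 days on every reading of the current text. Other assumed windows would bring it to 3 or 14 days.

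**Age of the result by the end of dosing, with no repeat**

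- Standard course: 28 + 14 = about 42 days.
- With the extension: 28 + 14 + 7 = about 49 days.

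**Does any other provision confirm status before the first dose?**

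- Contraception (3.1.7) is an agreement to use it. It is not a check.
- Self-report (3.1.7) depends on the woman knowing or suspecting.
- Section 5.6 allows treatment to stop when changes in her condition "render the patient unacceptable for further treatment in the judgment of the investigator". That acts once exposure has begun.
- The repeat-laboratory clause is tied to deterioration.
- The Week 1, Week 2 and surgery visits come after the first dose and schedule no pregnancy test.

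None of these does so.

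**Number of women who would need a moved or repeated test under a 7-day window**

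- Under 5.1, only those whose test would be 8-28 days old at first dose.
- Under the literal calendar reading, the minimum age of 14 days exceeds 7, so every woman of child-bearing potential.
- Upper bound at planned accrual: 9 women × 1 = 9. Lower bound: 0.

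**The case against.** The best case against is that this is a preference and not an error. The plan sets a uniform four-week window for laboratory work, breaks none of its own rules in doing so, and contains nothing that makes 28 days wrong or 7 days right. It handles a new conception through contraception, whose agreed period spans the gap between test and dose, and through immediate notification. Harm therefore needs conception after the test, contraceptive failure and no suspicion, all together, in a group that may contain nobody.

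The teratogenicity clause is also weak support. It refers to other therapeutic agents in the trial although HCQ is the only study drug in 5.2, and the HCQ-specific sentence beside it says the effects are unknown. The remedy is partial as well.

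Finally, section 4.3 states "The informed consent form is considered to be part of the protocol". The consent form was not available for this review and may set a timing.

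Most of this stands, and it is why the point is minor. No rule is breached, no probability of undetected pregnancy can be derived from the documents, and the choice of 7 days is a judgement. What does not follow is that the existing safeguards make the test's timing irrelevant, since none of them establishes status at the first dose. If the consent form already sets a tighter window, copying it into 5.1 and the calendar would still help, because those are the sections that give the screening and visit timing.

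**Conclusion.** The point holds as a minor, precautionary improvement to patient safety. The plan permits a first dose on a negative pregnancy test up to 28 days old, with no repeat required in the text available. A 7-day window would lower that maximum by 28 − 7 = 21 days. This is a change in the permitted age of a test; the documents give no basis for turning it into a change in risk. Between 0 and 9 of the 18 planned patients are concerned. The primary endpoint, sample size and analysis are untouched.

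The conclusion rests on two conditions: that the general baseline windows govern the pregnancy test, and that the consent form sets no tighter timing.

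**What to change.** Add the pregnancy test to section 5.1 and footnote its calendar row so that it overrides the general baseline window. Suggested wording: *Women of child-bearing potential must have a negative pregnancy test within 7 days before the first dose of HCQ; repeat the test if the first dose falls outside this window.* The investigators should confirm the 7 days; 3 or 14 are alternatives.

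The text cost is one line and one footnote, plus one simple test done later or repeated. The practical cost is a possible added contact. The calendar runs from Pre-Study to Week 1 (D7) with no Day 1 column, so a woman screened more than 7 days before dosing needs a brief visit, for example when the drug is dispensed. That is at most 9 such contacts in the whole trial. The pharmacokinetic text in 9.1 mentions a draw on day 1 of week 1. If the site runs that visit, the test could be done there before dosing at no extra contact, but the calendar puts the first on-treatment draws at day 7, so this cannot be relied on.

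The change shortens only the gap between test and first dose. It does not cover conception during the 14-21 days of dosing, or one too recent to detect.

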5.2 Agent Administration

Treatment will be administered on an outpatient basis. Reported adverse events and potential risks are described in Section 7. Appropriate dose modifications are described in Section 6. No investigational or commercial agents or therapies other than those described below may be administered with the intent to treat the patient's malignancy.

| Dose Schedule | |
|------------------------|------------------------------------|
| Dose Level | Dose |
| | Hydroxychloroquine (mg/day) |
| Level -1 | 200 mg/day |
| STARTING DOSE: Level 1 | 400 mg/day |
| Level 2 | 800 mg/day |
| Level 3 | 1200 mg/day |

Subjects will receive HCQ every day for 14 days, starting at least 14d before planned surgery and optimally ending day prior to surgery. Dosing can be extended 7 days if necessary due to unexpected delays. HCQ can be taken at any time of the day with meals. Tablets of HCQ are available in 200 mg strengths. HCQ will be administered in divided doses (twice a day) for doses above 200 mg/day to minimize nausea. The divided doses should be taken in the AM and at night with meals. Subjects will also be required to keep a medication diary and to present this at the end of the treatment. Should a subject have emesis and regurgitate the medication within 30 minutes of taking it, the dose may be repeated once, but if vomiting occurs longer than 30 minutes after ingestion, the dose should not be repeated. Subjects taking antacids, proton-pump inhibitors or H2-blockers should not take hydroxychloroquine within 4 hours of these medicines.

5.3 See Statistical Considerations for description of Dose-Escalation Process

An adaptive, nonparametric, isotonic regression model will be employed in order to determine the biological effect of HCQ as well as to assess safety. Patients will be enrolled starting at dose level 1. Dose escalation and de-escalation is described in detail in the Statistical Considerations section below. Briefly,

1. Treat a cohort of 3 patients at dose level 1
2. Let j^t denote the highest level tried thus far. At the current dose level j , based on the observed data, determine the dose j^* that has the highest isotonic estimate of biological effect probability among the tried doses.
3. If $j^* > j$, escalate to dose $j+1$
4. If $j^* < j$, de-escalate to dose $j-1$
5. If $j^* = j < j^t$, stay at dose level j ; otherwise if $j^* = j = j^t$, escalate to dose $j+1$

Once the maximum sample size is reached ($n = 18$), select the lowest dose that has the highest estimate of biological effect based on PAR-4 levels.

5.4 Definition of Dose-Limiting Toxicity

Subjects will be evaluated for toxicity according to the Common Terminology Criteria for Adverse Events (CTCAE) of the National Cancer Institute (NCI) version 4.0 available at: www.ctep.gov. A DLT is defined as any of the below treatment emergent toxicities with attribution (possibly, probably or definitely related) to the study medication that occurs during or within 30 days of the last dose of hydroxychloroquine.

Non-Hematologic:

- \geq Grade 3 or 4 neuropathy
- \geq Any Grade 3 or 4 adverse event (excluding grade 3 nausea, vomiting, diarrhea lasting < 7 days or grade 3 fatigue). Note: Abnormal non-hematologic laboratory values $>$ grade 3 will be considered a DLT if they are determined to be clinically significant and possibly, probably or definitely related to study drug. If baseline value is elevated (or decreased) prior to enrollment, an increase (or decrease) will not be considered a DLT unless it worsens by 2 grades and is determined to be clinically significant by the treating investigator.
- \geq Grade 3 nausea, vomiting, or diarrhea lasting > 7 days despite maximal antiemetic/antidiarrheal therapy
- Grade 5 toxicity

Hematologic:

- Grade 4 neutropenia ($ANC < 0.5 \times 10^9/L$) lasting for ≥ 7 days
- Febrile neutropenia ($ANC < 1.0 \times 10^9/L$ with a fever $\geq 38.3^\circ C$)
- Grade 4 thrombocytopenia (platelets $< 25.0 \times 10^9/L$) lasting ≥ 7 days despite dose delay
- Grade 3-4 thrombocytopenia associated with bleeding
- Grade 5 toxicity

Management and dose modifications associated with the above adverse events are outlined in Section 6.

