5.7 Duration of Follow Up

Patients will be followed for 30 days after surgery or 30 days after completion of the last dose of hydroxychloroquine if no surgery is completed. Patients removed from study for unacceptable adverse event(s) will be followed until resolution or stabilization of the adverse event. Follow-up visit should be combined with subject standard of care post-operative visit. If that visit occurs prior to the 30 days post op, subject should be contacted 30 days or after completion of the last dose for adverse event assessment.

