7.4 Adverse Event Characteristics

- **CTCAE term (AE description) and grade:** The descriptions and grading scales found in the revised NCI Common Terminology Criteria for Adverse Events (CTCAE) version 4.0 will be utilized for AE reporting. All appropriate treatment areas should have access to a copy of the CTCAE version 4.0. A copy of the CTCAE version 4.0 can be downloaded from the CTEP web site http://ctep.cancer.gov/protocolDevelopment/electronic_applications/ctc.htm.
- **For expedited reporting purposes only:**
 - AEs for the agent(s) that are listed above should be reported only if the adverse event varies in nature, intensity or frequency from the expected toxicity information which is provided.
 - Other AEs for the protocol that do not require expedited reporting are outlined in the next section (Expedited Adverse Event Reporting) under the sub-heading of Protocol-Specific Expedited Adverse Event Reporting Exclusions.
- **Attribution of the AE:**
 - Definite – The AE *is clearly related* to the study treatment.
 - Probable – The AE *is likely related* to the study treatment.
 - Possible – The AE *may be related* to the study treatment.
 - Unlikely – The AE *is doubtfully related* to the study treatment.
 - Unrelated – The AE *is clearly NOT related* to the study treatment.

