Blood samples for pharmacokinetic analysis will be collected prior to the start of HCQ regimen and during day 1 of weeks 1 and 2 and on/after day of surgery (+/- 1 day), as specified in the Study Calendar. Blood samples (4 mL) will be collected in heparinized tubes. After collection, blood and anti-coagulant will be mixed by inverting the tube 8–10 times and samples will be placed on ice immediately. Further processing will be carried out in the bioanalytical lab by staff in the Center of Pharmaceutical Research and Innovation (CPRI) under the direction of [name]. Concentrations of HCQ and metabolites will be quantified using a validated bioanalytical assay implemented for LC/MS/MS.

Shipping of Specimens for Pharmacokinetics

Samples will be collected by study personnel and will be forwarded to the CPRI for storage, processing and analysis.

Tumor Collection for Pharmacodynamics

If available, Diagnostic biopsies and paired resected tumor specimen will be store in formalin-fixed, paraffin-embedded blocks for potential autophagy and apoptosis analysis in the future. Each subject will sign the consent form for tissue collection before enrolled in the study.

Shipping of Specimens for Pharmacodynamics

Samples will be collected by study personnel in [name] lab for storage, processing and analysis. For PK/Par-4 sample pick up contact [name] at [contact].

Site(s) Performing Correlative Study

University of Kentucky.

STUDY CALENDAR

Baseline evaluations are to be conducted within 2-4 weeks prior to start of protocol therapy. In the event that the patient's condition is deteriorating, laboratory evaluations should be repeated more frequently, as clinically indicated. Study drug administration should begin optimally 2 weeks prior to date of surgery and continue until day prior to surgery. Dosing can be extended one week if necessary for any unanticipated delays.

| Studies to be obtained | Pre-Study | Week 1 (D7) | Week 2 (D14) | Day of Surgery | Post-operative visit | Off study |
|---|------------------|--------------------|---------------------|-----------------------|-----------------------------|------------------|
| History | X | X | X | | X | X |
| Physical Exam with vital signs | X | X | X | | X | |
| Height, Weight | X | | | | | |
| Performance Status | X | | | | | |
| CBC, differential, platelets | X | X | X | | X | |
| CMP | X | X | X | | X | |
| Pregnancy test (only females of childbearing potential) | X | | | | | |

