11.5 Analysis of Safety

All patients who received study drug will be included in the safety analysis of this study. Adverse event data and corresponding toxicity grades during the days of treatment will be summarized in each tumor cohort and in the overall patient population. Incidence tables will be generated to summarize incidence of patients reporting at least one episode of each specific adverse event, incidence of adverse events causing withdrawal and incidence of serious adverse events. The total number of episodes for each event reported (Frequency Table), the severity and attribution to study therapy of each episode reported (Severity Table and Attribution Table) will also be displayed.

Listings of adverse events by patients will include the time to onset, the duration of each event, the severity of each event, and the relationship of the event to study therapy, whether it was a serious event, and whether it caused withdrawal. Safety data will be summarized for the overall patient group and by tumor cohort. Toxicities will be graded according to Common Toxicity Criteria (CTCAE) v4.0.

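### On the optimal schedule about two-thirds of the DLT window falls after resection, and neither the attribution scale nor the Section 11.5 tables separate operative events from hydroxychloroquine toxicity

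*Combined protocol and SAP*

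**What the plan says.** **DLT definition (5.4).** A DLT is one of a list of "treatment emergent toxicities with attribution (possibly, probably or definitely related) to the study medication". The same sentence sets the time limit, and an event qualifies only if it is one "that occurs during or within 30 days of the last dose of hydroxychloroquine". On the non-hematologic side, any Grade 3 or 4 event qualifies apart from short-lived Grade 3 gastrointestinal events and Grade 3 fatigue. Laboratory abnormalities must also be clinically significant. An abnormal laboratory baseline is judged on the value before enrollment; nothing re-sets it after surgery.

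**Attribution (7.4).** The five categories all concern study treatment. The lowest that counts toward a DLT is Possible: "The AE *may be related* to the study treatment". There is no category or field for relation to surgery.

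**Timing (5.2 and Study Calendar).** Section 5.2 sets the schedule: "Subjects will receive HCQ every day for 14 days, starting at least 14d before planned surgery and optimally ending day prior to surgery". It also allows a further week of dosing when surgery is unexpectedly delayed. The Study Calendar agrees: "Study drug administration should begin optimally 2 weeks prior to date of surgery and continue until day prior to surgery".

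**Follow-up (5.7).** "Patients will be followed for 30 days after surgery", or 30 days after the last dose if there is no operation.

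**Safety analysis (11.5).** The adverse event and grade summary is confined to the treatment days and is given by tumor cohort and overall. The tables also show "the severity and attribution to study therapy of each episode reported". Per-patient listings include time to onset, duration, severity and relation to study therapy.

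**Use of toxicity (11.1, 11.3).** The acceptable toxicity rate is at most 30%, and 11.3 says the design incorporates toxicity. The numbered steps in 5.3 and 11.1 mention only biological effect.

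**The concern.** Every patient is enrolled with a resection planned, and on the intended schedule the operation comes the day after the last dose. The 30-day tail of the DLT window is then almost exactly the first 30 post-operative days. Several reactions that 7.3 lists for hydroxychloroquine (abdominal pain, nausea, vomiting, anemia, thrombocytopenia, abnormal liver tests, hypoglycemia) can also follow an operation. An assessor may find it hard to go below Possible for such an event, and Possible is enough for a DLT.

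At stake is the reading of the DLT rate against the 30% limit, and of the toxicity profile, which is a secondary objective (1.2.1). Eligibility covers any resectable solid tumor, including primary brain tumors, with no stratification (11.4) and no control arm. Dose levels holding a few patients each may therefore contain different operations. A difference in DLT rate between levels could partly reflect that mix.

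One would expect 11.5 to let the reader see this. As written, its summary stops at the end of treatment, so it omits most of the post-operative part of the DLT window. It also has no dose-level table.

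**Working it through.** The plan gives no figure for the post-operative share of the window, so there is nothing to reproduce.

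**1. Share of the window after surgery**

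Inputs: 14 dosing days, or 21 with the extension (5.2); 30 days after the last dose (5.4); surgery optimally the day after the last dose (5.2, Study Calendar). Share = post-operative days / (dosing days + 30). The lower value leaves out the day of surgery and the higher value counts it.

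| Schedule | Window (days) | Post-operative days | Share |
|---|---|---|---|
| 14 days, surgery on day 15 | 14 + 30 = 44 | 29-30 | 66-68% |
| 21 days, surgery on day 22 | 21 + 30 = 51 | 29-30 | 57-59% |
| 14 days, surgery a week late (day 22) | 44 | 22-23 | 50-52% |

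**2. Are the events collected?**

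With surgery on day 15, the 5.7 follow-up runs to day 15 + 30 = 45, and the DLT window ends on day 44. With surgery on day 22 after 14 days of dosing, follow-up runs to day 52. Follow-up therefore covers the DLT window. The gap lies in attribution and tabulation.

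**3. What the 11.5 summary covers**

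Read literally, it covers 14 of the 44 days (14/44 = 32%), all before surgery on the optimal schedule.

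**4. Illustration of size (assumption)**

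Let d be the true drug DLT rate; 10% and 20% are among the toxicity rates simulated in Table 1. Let s be the proportion of patients with a post-operative Grade 3-4 event that is surgical in origin but rated at least Possible. The documents give no value for s; 2.5-20% is assumed. Taking the two as independent, observed rate = 1 - (1 - d)(1 - s).

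| s | d = 10% | d = 20% |
|---|---|---|
| 2.5% | 1 - 0.90 × 0.975 = 12% | 1 - 0.80 × 0.975 = 22% |
| 5% | 1 - 0.90 × 0.95 = 14.5% | 1 - 0.80 × 0.95 = 24% |
| 10% | 1 - 0.90 × 0.90 = 19% | 1 - 0.80 × 0.90 = 28% |
| 20% | 1 - 0.90 × 0.80 = 28% | 1 - 0.80 × 0.80 = 36% |

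The value of s that brings the observed rate to 30% is 1 - 0.70/(1 - d): 22% for d = 10% and 12.5% for d = 20%.

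**5. At cohort level**

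One DLT in a cohort of 3 is 33%, above 30%. For d = 10%, the chance of at least one DLT in three patients is 1 - 0.90³ = 27%. At observed rates of 12.25% and 28% it is 1 - 0.8775³ = 32% and 1 - 0.72³ = 63%. These are chances of seeing an event. The documents attach no decision to it.

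**The case against.** **Attribution already filters.** Events rated Unlikely or Unrelated are not DLTs, so a clear operative complication drops out. This stands. The problem is confined to ambiguous events, and an assessor who uses the lower categories freely will keep it small.

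**The split can be recovered.** The 11.5 listings give time to onset for each patient. With 18 patients and known surgery dates, a before-and-after table could be built later. This also stands, so it would be wrong to say the plan makes separation by period impossible. The split is not pre-specified, however, and relation to surgery is not recorded at all. Reconstructing that afterwards would be weaker than recording it at the time.

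**Tumor site is already shown.** Section 11.5 summarises safety by tumor cohort. That helps with differing operations, but without dose level it does not show which operations lie behind the DLT rate at a given dose.

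**The size is assumed.** No document supports any value of s. In the table above, seven of the eight results stay below 30%; only d = 20% with s = 20% exceeds it.

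A reader might infer more than the documents support in two ways. The first is that two-thirds of the DLTs will be surgical: share of days is not share of risk, and the two-thirds applies only to the optimal schedule. The second is that misattributed events will change the selected dose. The steps in 5.3 and 11.1 use only the estimate of biological effect. Although 11.1 and 11.3 mention 30%, no toxicity cut-off or rule is written, so an effect on dose selection can be neither shown nor computed.

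**Conclusion.** The concern holds as a problem of interpretation and reporting. On the optimal schedule 66-68% of the DLT window is post-operative (57-59% with the extension, 50-52% if surgery is a week late). A rating of Possible is enough for a DLT, and nothing records relation to surgery. Ambiguous post-operative events can therefore enter the DLT rate as hydroxychloroquine toxicity. By how much is unknown: the 12-28% and 22-36% ranges rest wholly on the assumed 2.5-20% and on independence of drug and surgical events.

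Section 11.5 does not resolve this. Its summary period is shorter than the windows in 5.4 and 5.7, and it has no view by dose level. The change is worth making because the toxicity profile is a stated objective. The case does not rest on any demonstrated effect on escalation or dose selection.

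**What to change.** 1. Reconcile the reporting period in 11.5 with 5.4 and 5.7, so that the safety tables cover the whole DLT window. State how events are reported if they fall after that window but within the 5.7 follow-up.
2. In 11.5, tabulate DLTs and Grade 3 or higher events by dose level in two periods: first dose to incision, and incision to the end of the 30-day window. Patients who have no operation need a stated place in the table.
3. Add one CRF field, relation to surgery, for events after incision, completed alongside the existing attribution to study treatment.
4. Leave the DLT definition and window in 5.4 unchanged. Show the DLT rate against the 30% limit with both periods displayed.

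The cost is one CRF field and one extra table. With 18 patients spread over the dose levels, the split is descriptive only and supports no formal comparison.
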